9.2.2.4 Outcome

The Investigator will follow up all AEs wherever possible until they have attained an acceptable outcome (Section 9.2.2.5).

The date of the outcome will be recorded, and the course of the AE will be assessed in accordance with the following classification:

- Recovered/resolved: the AE has resolved, and the participant returned to their condition prior to onset
- Recovered/resolved with sequelae: the AE resolved, but the participant has sequelae
- Recovering/resolving: the AE has almost resolved, and the participant is returning to his condition prior to onset
- Death: the participant died
- Not recovered/not resolved: the AE had not resolved, and the participant’s condition remained unchanged at the last time of observation. In case of death from a different cause, events ongoing at the time of death will be classified as such.

9.2.2.5 Action taken and follow-up of events

All adverse events must be followed up by the Investigator until:

- the event is resolved, or
- no further medically relevant information in relation to the event can be expected, and
- the Investigator considers it justifiable to terminate the follow-up.

Events that are ongoing at the time of the participant’s EOS visit should be indicated as “not recovered/not resolved” or “recovering/resolving” (whichever applicable) if considered unrelated to the study drug. AEs that are considered related to the study drug and are ongoing at the time of the participant’s EOS visit should continue to be followed up by the Investigator until the event has resolved or the Investigator, Sponsor and Medical Monitor consider it justifiable to terminate the event follow-up.

All AEs should be treated appropriately. The Investigator will decide upon the appropriate action to be taken in response to an AE, which may include one or more of the following:

- no action taken (i.e., further observation only)
- administration of a concomitant medication or other treatment

- hospitalisation or prolongation of current hospitalisation (event to be reported as an SAE)
- other.

9.2.3 Reporting of serious adverse events

The Investigator will report all SAEs to the Sponsor (or their pharmacovigilance vendor) within 24 hours of the site personnel becoming aware of the event in accordance with the procedures described in the Safety Management Plan. The report should be in writing by email with the Medical Monitor on copy and documented on a standard SAE Reporting Form. In addition to this, fatal or life-threatening SAEs must be reported immediately to the Sponsor (or their pharmacovigilance vendor) and the Medical Monitor, irrespective of the extent of available AE information.

For all SAEs, the Investigator is obligated to pursue and provide information in accordance with the timeframes for reporting specified above. In addition, an Investigator may be requested to obtain specific additional follow-up information in an expedited fashion. This information may be more detailed than that captured on the AE case report form. In general, this will include a description of the AE in sufficient detail to allow for a complete medical assessment of the case and independent determination of possible causality. Information on other possible causes of the event, such as concomitant medications and illnesses must be provided. In the case of a participant death, a summary of autopsy findings (if available) must be submitted as soon as possible to the Sponsor.

All SAEs will be followed up until resolution, or until in the opinion of the Principal Investigator and the Medical Monitor, no further improvement can be reasonably expected on medical grounds.

The IRB/EC(s) and Regulatory Authority will be notified of all SAEs in accordance with their requirements.

Reporting and follow-up procedures are described in the Safety Management Plan.

9.2.4 Pregnancy

All women of reproductive potential will agree to remain on effective contraception for the duration of the study. While all efforts will be undertaken to prevent pregnancy among participants during this time, should a participant become pregnant during the study (at any stage), she will be counselled regarding the unknown risks associated with administration of molnupiravir, and will undergo a further informed consent process to confirm her continued participation in the study, and willingness to be followed through the pregnancy and for three months thereafter.

Pregnancies occurring in participants enrolled in this study must be reported. Follow-up will include, but is not limited to, the following:

- Ultrasound at approximately 20 weeks' gestation
- Pregnancy complications
- Outcome ascertainment
- Information related to live births
- Follow-up of infants to approximately 3 months of age.

Reporting will be performed using a standard Pregnancy Reporting Form. The reporting procedure follows that described for SAEs in Section 9.2.3.

Pregnancy alone is not regarded as an AE. Elective abortions without complications should not be considered AEs unless they were therapeutic abortions. Hospitalisation for normal delivery of a healthy newborn should not be considered an SAE. Pregnancy is not considered an SAE unless there

is an associated outcome that meets one or more of the SAE criteria. Spontaneous abortions should always be reported as SAEs.

Any pregnancy outcome considered to be an SAE should be reported within the timelines and using the procedures described in Section 9.2.3.

10. STATISTICAL CONSIDERATIONS

This section describes the planned analysis of study objectives as envisioned at the time of writing the protocol. Details of these analyses and their presentation, and any substantive changes to these planned analyses, will be documented in a detailed Statistical Analysis Plan (SAP) developed and approved prior to enrolment of the first participant.

10.1 Sample Size Determination

This study has been powered around a reduction from 6% to 4% in hospitalisation/death rates between the arms. This would give a 33% reduction, the approximate effect size seen in the registration MOVE-OUT trial¹².

With 1863 patients per arm, there would be 80% power to detect a reduction in hospitalisations from 6% to 4% in a single final analysis. A 5% overage to account for loss to follow up has been added, resulting in a total sample size of 2000 patients per arm. The interim (e.g., at 1000/arm) would need to use a Peto rule ($p<0.001$) to preserve statistical power for the final analysis.

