
	drug reactions, effectiveness through time to resolution of symptoms and progression to severe disease (requiring hospitalisation and/or resulting in death), and adherence.
Design	
This is a multi-centre, double-blind, Phase 3 study to observe the effectiveness, safety, and tolerability of molnupiravir 800 mg administered 12-hourly for five days to adult patients with mild COVID-19 at the time of enrolment who are at risk of progression to severe disease, compared to a placebo.
 
Patients with recent onset of COVID-19 symptoms will be screened to assess eligibility for enrolment. Confirmation of SARS-CoV-2 infection will be performed through rapid antigen detection using the LumiraDx™ point of care diagnostic platform. Eligible patients will be enrolled and will be randomised in a 1:1 manner to start treatment with either molnupiravir or a placebo on the same day. Patients will record their symptoms (through a self-administered questionnaire) and self-observed vital signs daily for 10 days from the time of enrolment and will be contacted by study team personnel on Days 3, 6 and 10 to monitor their well-being. Adverse event and concomitant medication data will be collected. A final end-of-study follow-up visit will be conducted on Day 29.
 
An independent Data and Safety Monitoring Board (DSMB) will be convened for this study with expertise in COVID-19 or respiratory viruses, and emerging epidemics. The purpose of the DSMB is to monitor the study for safety and operational futility.
 
In addition to the usual, regular, required reporting to SAHPRA, we anticipate that additional reporting may be required, noting the severity of the 3rd and 4th waves, the level of "breakthrough" infections in the context of high background comorbidities, and the urgent interest in this class of drugs.

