4.3 Study Pausing Rules

The occurrence of any serious adverse event (SAE) considered related to the study drug will prompt a halt to further enrolment into the trial pending a formal safety review by the DSMB.

Dosing of on-study participants, and follow-up of participants previously enrolled and dosed, will not be altered unless, for example, additional safety measures are judged to be required following the safety review.

The DSMB will provide recommendations to the Sponsor regarding study stopping or continuation or amended circumstances under which the study may proceed as detailed in the DSMB Charter. Additional investigations or assessments may be recommended to establish causality or ensure ongoing safety of enrolled participants.

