6.1.3 Blinding

The study will be double-blind. Neither the participants nor the principal investigator (or designee) who will be assessing AEs, will know the treatment group. A participant's treatment assignment may only be unblinded when knowledge of the treatment is essential for the safety of the participant and following consultation with the medical monitor. The process for unblinding will be documented in a Study Unblinding Plan.

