9.1.5 Safety Review Team

The SRT will comprise at least the following personnel:

- the Principal Investigator
- the Medical Monitor
- the Safety Physician
- another medically qualified physician, virologist, or immunologist.

The members of the SRT are responsible for decisions relating to participant safety and study continuation.

The timing of other SRT data reviews and a detailed description of the operational aspects of the SRT will be documented in the SRT Charter.

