13.4 Discontinuation of the Study

[name], the Sponsor, the Funder, the Principal Investigator, IRB/EC(s) and Regulatory Authority independently reserve the right to discontinue the study at any time for safety or other reasons. This will be done in consultation with the Funder, Sponsor and Principal Investigator where practical. In the event of premature termination or suspension of the study, the above-mentioned parties will be notified in writing by the terminator/suspender stating the reasons for early termination or suspension (with the exception of the Sponsor's responsibility for notifying the Regulatory Authority). Following such a decision, the Sponsor and the Investigator will ensure that adequate consideration is given to the protection of the participants' interest and safety. All ongoing participants will be followed up for a minimum of 28 days post initiation of the study drug and will be scheduled for an EOS visit. At this visit all assessments scheduled in accordance with the SOE (Section 1) will be performed (with the addition of safety laboratory samples if considered necessary due to safety considerations).

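### Does a p<0.001 interim in Protocol Section 10.1 contradict a DSMB remit limited to safety and operational futility?

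*Protocol*

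**What the plan says.** Section 10.1 of the protocol opens with the design effect: "This study has been powered around a reduction from 6% to 4% in hospitalisation/death rates between the arms". It then claims, for 1863 patients per arm, "80% power to detect a reduction in hospitalisations from 6% to 4% in a single final analysis". A 5% allowance for loss to follow-up is added and the size is given as 2000 per arm. The last sentence introduces an interim: "The interim (e.g., at 1000/arm) would need to use a Peto rule". The threshold is p<0.001, and the reason given is to protect the final analysis.

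The synopsis, Section 4.1 and Section 9.1.6 all carry the same sentence: "The purpose of the DSMB is to monitor the study for safety and operational futility".

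Other provisions bear on stopping:

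- Section 4.3 has one pausing trigger: "The occurrence of any serious adverse event (SAE) considered related to the study drug will prompt a halt to further enrolment". It also has the DSMB recommend stopping or continuing, with the detail in its Charter.
- Section 9.1.5 says of the Safety Review Team: "The members of the SRT are responsible for decisions relating to participant safety and study continuation". The team includes the Principal Investigator, who is blinded under Section 6.1.3: "Neither the participants nor the principal investigator (or designee) who will be assessing AEs, will know the treatment group".
- Section 13.4 lists several parties who "independently reserve the right to discontinue the study at any time for safety or other reasons".
- Section 9.1.6 puts a biostatistician on the DSMB, provides for scheduled meetings, and leaves its objectives and responsibilities to a Charter ratified before the study starts.
- The introduction to Section 10 leaves analysis detail to an SAP approved before the first enrolment.

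**The concern.** The interim sentence stands in the paragraph that powers the primary comparison, and its stated reason is to protect the final analysis. That is how one writes about an efficacy boundary. Yet the power statement is for one final analysis, and the only independent body with a monitoring role has a purpose, given three times, that does not include efficacy. Neither the pausing rule, the Safety Review Team nor the general right to discontinue assigns anyone to compare the arms on efficacy.

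Read this way, the protocol leaves it unclear whether the primary endpoint is tested once or twice, and who would see unblinded outcome data and act on them. If the trial stopped on such a look, the decision might be attacked as falling outside the board's stated remit. An unplanned second test could also, in principle, inflate the type I error or reduce power.

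**Working it through.** **Inputs.** From Section 10.1: 6% against 4%, 1863 per arm, 80% power, 2000 per arm enrolled, interim at about 1000 per arm, p<0.001. From Section 6.1.2: 1:1 allocation. Section 10.1 states neither alpha nor sidedness, so two-sided 0.05 is assumed. One interim look is assumed.

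**1. The plan's own figure.** With the pooled-variance formula and mean rate 0.05:

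n = [1.960·√(2·0.05·0.95) + 0.8416·√(0.06·0.94 + 0.04·0.96)]² / 0.02²

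= [1.960·0.30822 + 0.8416·0.30790]² / 0.0004

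= 0.86323² / 0.0004 = 1862.9, that is 1863 per arm.

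This matches the protocol. A one-sided test gives 1468 and a continuity-corrected two-sided test 1962, so the assumed alpha and sidedness fit the stated figure.

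**2. What crossing would take.** Two-sided p<0.001 corresponds to |z| > 3.2905. At 1000 per arm the standard error of the difference is √(2·0.05·0.95/1000) = 0.00975, so the observed difference must exceed 3.2905·0.00975 = 0.0321, about 3.2 percentage points.

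In event counts, with 60 control events in 1000:

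| Molnupiravir events | Pooled z-test | Fisher's exact | Continuity-corrected chi-square |
|---|---|---|---|
| 29 | 0.00077 | 0.00103 | 0.00114 |
| 30 | 0.00121 | 0.00162 | 0.00176 |
| 40 (planned effect) | 0.040 | 0.051 | 0.051 |

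The limit is therefore 29 events or one fewer, depending on the test. The planned effect would not stop the trial under any of the three.

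**3. Chance of crossing under the planned effect.** The expected z at 1000 per arm is 0.02/0.00975 = 2.052, and P(Z > 3.2905 − 2.052) = P(Z > 1.2385) = 10.8%.

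**4. Overall type I error with the look.** The interim and final statistics are bivariate normal with correlation √(1000/N). The error is 1 − P(|Z₁| ≤ 3.2905 and |Z₂| ≤ 1.960):

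- N = 1863, correlation 0.733: 0.0502.
- N = 2000, correlation 0.707: 0.0502.

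A final level of 0.0498 would give exactly 0.05.

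**5. Power with and without the look** (final test at 0.05, same normal approximation):

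| Per arm at the end | One analysis | With the look |
|---|---|---|
| 1863 | 80.0% | 80.0% |
| 1900 (2000 less 5%) | 80.7% | 80.8% |
| 2000 | 82.7% | 82.7% |

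**6. The passages side by side.** Section 10.1 says what an interim would need, with an example of when. It does not say that the trial will stop for efficacy, and no other section says that it may or may not. Basing power on one final analysis does not conflict with a look this strict, because step 5 shows that the look leaves power where it was.

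Section 9.2.1 counts death and hospitalisation as serious adverse events and expressly includes those due to COVID-19. The events of the primary endpoint are thus also safety events within the DSMB's stated purpose. A stringent threshold on a comparison of those events can sit within that purpose, as a guard against harm or against over-reading early data.

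**The case for a change.** The strongest reply is that a p<0.001 boundary justified by protecting the final analysis is, on its natural reading, an efficacy boundary. On that reading operational futility does not cover it, and a Charter that added efficacy would go beyond a purpose stated three times. The definite article also presupposes an interim that no other section describes. A chance of about one in ten of crossing under the design assumption is not trivial, and it would be the blinded trial's most consequential decision.

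Part of this stands. The interim sentence is loosely worded: it does not say whether the look is for benefit, for harm, or not firmly planned, and the purpose sentence was not written with it in mind. The harm reading is possible but fits the stated reason less well.

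The step from there to a contradiction does not stand. No two statements in the protocol exclude each other. The threshold is in the protocol, so a decision that used it would not rest on a rule invented afterwards. Who reviews what, the timing and the final significance level commonly sit in a Charter and an SAP. The protocol sends the DSMB's responsibilities and the analysis detail to those two documents, both to be settled before the study or enrolment starts. Neither is at hand, so their silence cannot be assumed.

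**Conclusion.** This is a small wording mismatch between Section 10.1 and the DSMB purpose sentence, and it does not call for a change to the plan. A team that takes one final analysis and a team that takes one look at p<0.001 both end with a type I error of about 5% (0.0500 or 0.0502) and 80.0% power at 1863 per arm. Deciding which reading was meant would alter no sample size and correct no bias. The Charter and SAP are the ordinary place to record it.

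The figures assume two-sided 0.05, a single look at about 1000 per arm and a normal approximation. The count needed to cross also depends on the test, which Section 10.1 does not name. The conclusion does not depend on that choice.

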10.2 Analysis Populations

For analysis purposes, the following populations are defined and will be described in greater detail in the trial Statistical Analysis Plan (SAP):

Population	Description
Full Analysis Set (FAS)	All enrolled participants.
Safety Analysis Set (SAF)	All enrolled participants who received a dose of the study drug.
Intention to Treat (ITT)	All enrolled randomized participants.
Per Protocol (PP)	All enrolled participants completing the study without major protocol deviations.

10.3 Analysis and Presentation of Data

10.3.1 General

10.3.1.1 Data summaries

All endpoints will be summarised overall and by risk factor. Continuous data will be summarised using descriptive statistics as appropriate (e.g., N, mean, standard deviation, median, range) and categorical data will be summarised using frequency tables (counts and percentages).

Baseline will be defined as the last available, valid measurement taken prior to initiation of the study drug.

Only data from protocol scheduled visits/time points will be included in “by visit” summary tables. Details of how data from unscheduled or out-of-window visits will be presented will be described in the SAP.

10.3.1.2 Handling of dropouts or missing data

No data imputation will be performed unless otherwise stated in the SAP.

10.3.2 Participant disposition

Participants enrolled, dosed, and completing the study will be summarised for the FAS, as well as reasons for withdrawal for all early withdrawals.

10.3.3 Participant demographics, baseline characteristics and concomitant medications

Demographic data, other baseline characteristics, prior (started prior to study drug administration) and concomitant medications (taken at the time of study drug administration or at any stage during the follow-up period thereafter) will be summarised for the SAF and ITT.

Some medications may be included in both the prior and concomitant medications summaries. Concomitant medications will be coded using the WHO Drug Dictionary (WHO-DD). The most recent released version at the time of study start will remain in effect throughout the study.

Medical and surgical history will be coded in accordance with the Medical Dictionary for Regulatory Activities (MedDRA) and summarised by system organ class and preferred term.

10.3.4 Efficacy data

Details of efficacy data analyses to be performed will be included in the SAP.

10.3.4.1

10.3.5 Safety data

All safety analyses will be performed for the SAF.

An overall summary of the number of participants with any AE, AEs considered related to study drug, SAEs, SAEs considered related to study drug, AEs leading to withdrawal of study drug, and AEs leading to withdrawal from the study will be presented.

AEs will be coded in accordance with MedDRA. The most recent released version of MedDRA at the time of study start will remain in effect throughout the study.

AEs will be summarised by MedDRA primary system organ class and preferred term. Summaries will be presented for overall incidence (number of participants and number of events), as well as by severity and relatedness to study drug.

Vital signs will be summarised. Absolute values and change from baseline will be presented.

All safety data will be listed.

10.3.6 Exploratory analyses

Details of exploratory endpoints and analyses to be performed will be included in the SAP.

11. STUDY MONITORING

Study conduct will be monitored by an independent monitor. Monitors will conduct remote monitoring and will visit the site as required. Review of individual participant records, including

consent forms, eCRFs, supporting data, laboratory specimen records, and endpoints through medical records (physicians' progress notes, nurses' notes) will be performed as detailed in the Clinical Monitoring Plan, to ensure protection of study participants, compliance with the protocol, and accuracy and completeness of records. The monitors also will inspect the site regulatory files to ensure that regulatory requirements are being followed, and the pharmacy to review product storage and management.

The Clinical Monitoring Plan will describe these activities and will take into consideration necessary adaptations to be made if physical access to the site is limited at any stage due to pandemic restrictions.

12. ETHICAL CONSIDERATIONS

12.1 Regulatory and Ethical Considerations

The study will be conducted according to GCP (including South African GCP Guidelines²⁴), the Belmont Report, the Declaration of Helsinki, and South Africa legal requirements regarding clinical trials. The study protocol and relevant supporting documents will be submitted for review and approval by the South African Health Products Regulatory Authority (SAHPRA) and the Human Research Ethics Committee (HREC) responsible for oversight of research conducted at the study site. The study protocol will be registered with the South African National Clinical Trial Registry (www.sanctr.gov.za), National Human Research Ethics Committee (www.ethicsapp.co.za) and www.ClinicalTrial.gov. Six-monthly progress reports will be submitted to SAHPRA and HREC for the duration of the study, and as requested. Upon completion or premature termination of the study, the Investigator will provide HREC and SAHPRA with a summary of the study's outcome, and any reports required.

